8.6 Follow-up of Adverse Events and Serious Adverse Events

8.6.1 Follow-up of Adverse Events with Onset during the Trial

During the trial, the investigator must follow up on each adverse event until it is resolved or until the medical condition of the subject is stable.

After the subject's last visit, the investigator must follow up on any adverse event classified as serious or considered to have a reasonable possible causality to the IMP until it is resolved or until the medical condition of the subject is stable. All such relevant follow-up information must be reported to Ferring. If the event is a chronic condition, the investigator and Ferring may agree that further follow-up is not required.

8.6.2 Collection of Serious Adverse Events with Onset after Last Visit in the Trial

If an investigator becomes aware of an SAE after the subject's last visit, and he/she assesses the SAE to have a reasonable possible causality to the IMP, the case will have to be reported to Ferring, regardless how long after the end of the trial this takes place.

9 STATISTICAL METHODS

This section details the planned statistical analysis of the primary endpoints and outlines the planned statistical analysis for the secondary endpoints. All analyses and further description of the statistical methodology for primary as well as secondary endpoints will be included in the statistical analysis plan (SAP). The SAP will be available before breaking the blind.

9.1 Determination of Sample Size

The sample size calculation is based on demonstrating superiority of quinagolide vaginal ring compared to placebo vaginal ring on the primary endpoint of changes in the sizes of endometrioma, DIE and adenomyosis lesions summed by type on MRI at cycle 4. An important assumption behind the sample size calculation is an equal magnitude of treatment effect for all three types of lesions. For example, for adenomyosis, by assuming an average baseline lesion size of 18 mm and a standard deviation of 4.5 mm,³⁹ a sample size of 24 randomised subjects (16 on active treatment and 8 on placebo) will have 83% power to detect a treatment effect difference of 6 mm (corresponding to a 33% reduction in lesion size) using a two-sample t-test at a 5% two-sided significance level. A similar assumption, i.e. the ratio between treatment effect and standard deviation is 4 to 3, is made for DIE and endometrioma to conclude 24 subjects to be randomised per sub-group. In total, 72 subjects will be randomised in this trial.

Table 9-1 summarises the required sample size in total for different assumptions of treatment effect difference and power.

Table 9-1 Sample Size by Treatment Effect Difference

Difference in the sum of lesion size reduction between quinagolide vaginal ring group and placebo vaginal ring group		Number of subjects in total ^a	
Absolute difference (mm)	Relative difference ^b (%)	Power 80%	Power 90%
4.5	25	39	51
5.0	28	33	42
5.5	31	27	36
6.0	33	24	30
6.5	36	21	27
7.0	39	18	24
7.5	42	15	21

^a Using a 2:1 randomisation and assuming a standard deviation of 4.5 mm.

^b Assuming an average baseline lesion size of 18 mm.

If the drop-out rate in any of the sub-groups are larger than 10%, the sample size of randomised subjects for that sub-group may be increased to up to 30.

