In this trial, there are three sub-groups of subjects, with each sub-group representing one sub-type of lesions, i.e. endometrioma, DIE and adenomyosis. Epidemiology studies have shown that endometriosis and adenomyosis can often coexist in the same subject.^{37,38} Since MRI can assess all pelvic compartments comprehensively at one time, it is feasible and convenient to examine any of the three sub-types of lesions presented in the subject in one MRI examination. The design of three separate sub-groups, with subjects on placebo in each sub-group, can ensure changes in each sub-

type of lesions are assessed against placebo and thereby help identify the sub-type of lesions that responds best to the treatment.

Although a multi-centre setting can help guarantee that the required number of subjects can be recruited within a reasonable time and also support the subsequent generalisation of the results, this trial is limited to a few trial centres with machines of high field strength (3T) and of limited brands to minimise variability of results. In addition, the standardisation of the MRI preparations, sequences and procedures in the trial-specific MRI manual, cross calibration among sites as well as the central reading and analyses of images by the same specialised laboratory have to a great extent been incorporated in the design of this trial to minimise variations across sites.

The treatment period of the trial lasts for four menstrual cycles, which approximately corresponds to the active treatment duration of 18-20 weeks in the second-look laparoscopy study, where significant reductions in endometriotic lesions were observed following oral administration of quinagolide up to 75 µg.

A non-hormonal single-barrier contraception method (i.e. condom) is required for subjects participating in the present trial. Condom is the only feasible contraception method in this trial, as other contraception methods such as oral contraceptives and intrauterine devices (IUDs) can potentially interfere with the assessment of lesions. Throughout the trial, contraception counselling and condoms will be offered to avoid occurrence of pregnancy during treatment. As a precautionary measure, a urine pregnancy test will be performed once per menstrual cycle in the present trial. If the test result is positive and is confirmed by a serum β hCG test, the subject will be discontinued from the trial immediately.

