4.5 Subject Replacement

A subject can only be assigned one screening number and one randomisation number. The screening and randomisation number are unique and cannot be re-used. Subjects who discontinue prematurely from the trial after randomisation are not to be replaced.

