$$\begin{cases} \mu_{QVR}^1 = \text{The mean change from baseline in the sum of the size of the endometrioma lesions at cycle 4 for QVR} \\ \mu_{QVR}^2 = \text{The mean change from baseline in the sum of the size of the DIE lesions at cycle 4 for QVR} \\ \mu_{QVR}^3 = \text{The mean change from baseline in the sum of the size of the adenomyosis lesions at cycle 4 for QVR} \\ \mu_{placebo}^1 = \text{The mean change from baseline in the sum of the size of the endometrioma lesions at cycle 4 for placebo ring} \\ \mu_{placebo}^2 = \text{The mean change from baseline in the sum of the size of the DIE lesions at cycle 4 for placebo ring} \\ \mu_{placebo}^3 = \text{The mean change from baseline in the sum of the size of the adenomyosis lesions at cycle 4 for placebo ring} \end{cases}$$

In order to control the overall type I error at 5%, the Hochberg procedure is implemented by ranking the 3 p-values in a decreasing order. If the largest p-value is ≤ 0.05 , superiority is established for all 3 types of lesions. If the largest p-value is > 0.05 , but the middle p-value is ≤ 0.025 , superiority is established for the two types of lesions with the smaller p-values. If the largest p-value is > 0.05 and the middle p-value is > 0.025 , but the smallest p-value is ≤ 0.0125 , superiority is established for only the type of the lesion with the smallest p-value. If the largest p-value is > 0.05 , the middle p-value is > 0.025 , and the smallest p-value is > 0.0125 , superiority is not established for any of the 3 types of lesions.

The primary analysis is based on the FAS including those missing the end-of-treatment MRI results. As described above, missing values will be imputed using a multiple imputation strategy.

Sensitivity Analyses

The following sensitivity analyses will be conducted:

1. To test efficacy in more perfect conditions:
 - The primary analysis in the PP population
2. To test sensitivity to missing data:
 - The primary analysis performed on completers (defined as subjects who have completed the scheduled treatment and have both a baseline and a cycle 4 MRI)
 - The primary analysis performed on subjects with both a baseline and an end-of-treatment MRI
 - The FAS using multiple imputation for missing data in a placebo-based pattern mixture model (based on a missing-not-at-random condition) as described by Ratitch

3. The primary analysis using the actual treatment rather than the planned treatment

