3.2 Data presentation

Due to the trial design including separate analysis of the primary endpoint for each of the three types of lesion (endometrioma, DIE and adenomyosis), some presentations will be performed by type of lesion, some will be performed for the three types of lesions combined, and some will be performed both by type and combined. Additionally, some presentations are also prepared by type of disease (i.e. endometriosis and adenomyosis), where the category of endometriosis combines endometrioma and DIE.

A subject will be included in the by type analysis if she has at least one lesion of that type ≥ 10 mm at baseline. Notice that a subject can be included in the analysis of more than one type of lesions.

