3.3 Determination of Sample Size

The sample size calculation is based on demonstrating superiority of quinagolide vaginal ring compared to placebo vaginal ring on the primary endpoint of changes in the sizes of endometrioma, DIE and adenomyosis lesions summed by type on MRI at cycle 4. An important assumption behind the sample size calculation is an equal magnitude of treatment effect for all three types of lesions. For example, for adenomyosis, by assuming an average baseline lesion size of 18 mm and a standard deviation of 4.5 mm [1], a sample size of 24 randomised subjects (16 on active treatment and 8 on placebo) will have 83% power to detect a treatment effect difference of 6 mm (corresponding to a 33% reduction in lesion size) using a two-sample t-test at a 5% two-sided significance level. A similar assumption, i.e. the ratio between treatment effect and standard deviation is 4 to 3, is made for DIE and endometrioma to conclude 24 subjects to be randomised per sub-group. In total, 72 subjects will be randomised in this trial.

Table 3-2 Sample Size by Treatment Effect Difference

Difference in the sum of lesion size reduction between quinagolide vaginal ring group and placebo vaginal ring group		Number of subjects in total ^a	
Absolute difference (mm)	Relative difference ^b (%)	Power 80%	Power 90%
4.5	25	39	51
5.0	28	33	42
5.5	31	27	36
6.0	33	24	30
6.5	36	21	27
7.0	39	18	24
7.5	42	15	21

a Using a 2:1 randomisation and assuming a standard deviation of 4.5 mm.

b Assuming an average baseline lesion size of 18 mm.

If the drop-out rate in any of the sub-groups are larger than 10%, the sample size of randomised subjects for that sub-group may be increased to up to 30.

The study was planned to be have a randomisation ratio of 2:1 with 2 subjects receiving quinagolide vaginal ring for each subject receiving placebo vaginal, however it was discovered, after LPLV but before database lock, that the randomisation list used during the study had a 1:1 ratio between quinagolide vaginal ring placebo vaginal ring. The use of a 1:1 ratio instead of a 2:1 ratio will increase the power to detect a difference between quinagolide vaginal ring and placebo vaginal ring.

4 Subject Disposition

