Secondly all monotone missingness is imputed, using a standard MAR based MI approach for monotone missingness, which imputes variables one at a time in the following order: the overall NRS score at visit 2, at visit 5, at visit 6, at visit 7, and at visit 8, and finally the sum of lesion sizes at end-of-treatment.

For each type of lesion and each imputation, the primary endpoint will be analysed using an analysis of covariance (ANCOVA) model, with the change in the sum of lesion sizes from baseline measured at end-of-treatment as the dependent variable, the baseline sum of lesions as covariate, and the treatment group as fixed effect. The treatment difference between active treatment versus placebo will be estimated for each of the three types of lesions.

Finally, the 100 different imputations are combined to an estimate of the treatment difference between active treatment versus placebo and its 95% confidence interval and corresponding p-value using SAS Proc Mianalyze.

In order to control the overall type I error at 5%, the Hochberg procedure is implemented by ranking the 3 p-values in a decreasing order. If the largest p-value is ≤ 0.05 , superiority is established for all 3 types of lesions. If the largest p-value is > 0.05 , but the middle p-value is ≤ 0.025 , superiority is established for the two types of lesions with the smaller p-values. If the largest p-value is > 0.05 and the middle p-value is > 0.025 , but the smallest p-value is ≤ 0.0125 , superiority is established for only the type of the lesion with the smallest p-value. If the largest p-value is > 0.05 , the middle p-value is > 0.025 , and the smallest p-value is > 0.0125 , superiority is not established for any of the 3 types of lesions.

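### Does the 83% power claim mislead because it ignores the Hochberg rule, the 1:1 allocation and drop-out?

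*Protocol*

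**What the plan says.** Protocol 9.1 sizes each lesion type separately. With a standard deviation of 4.5 mm, 16 subjects on active and 8 on placebo "will have 83% power to detect a treatment effect difference of 6 mm", using a two-sample t-test at two-sided 5%. The same ratio of effect to standard deviation, 4 to 3, is carried over to DIE and endometrioma. The section adds: "An important assumption behind the sample size calculation is an equal magnitude of treatment effect for all three types of lesions". SAP 3.3 repeats all of this. Table 9-1 in the protocol and Table 3-2 in the SAP give total sizes for other effects, with a footnote stating 2:1 randomisation.

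Superiority is declared by a different rule. In Protocol 9.6.2 "the Hochberg procedure is implemented by ranking the 3 p-values in a decreasing order". Both documents step through cut-offs of 0.05 and 0.025, and at the last step nothing is claimed unless the other conditions hold "but the smallest p-value is ≤ 0.0125" (SAP 9.2.1).

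On losses, Protocol 4.5 says: "Subjects who discontinue prematurely from the trial after randomisation are not to be replaced". Protocol 9.1 allows, but does not require, an increase to 30 in a sub-group whose drop-out exceeds 10%.

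On allocation, SAP 3.3 reports that the list used was 1:1 and comments: "The use of a 1:1 ratio instead of a 2:1 ratio will increase the power". It gives no figure.

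**The concern.** The 83% belongs to a single 5% test, but no lesion type is judged by a single 5% test. A type that responds alone will usually have to pass the smallest cut-off, 0.0125, which is a much harder test with 24 subjects. The 24 also carries no allowance for missing MRIs.

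The scenario of unequal response is not far-fetched. Protocol 3.5.1 says that the separate sub-groups "thereby help identify the sub-type of lesions that responds best to the treatment". The SAP remark that 1:1 raises power stands in the same section as the 83%, so a reader may infer that each type was tested with more than 83% power and read a non-significant type as good evidence of no effect. If that type were the only responder, the real figure could be nearer 71%, a 29% chance of missing a true 6 mm difference instead of the 17% implied.

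**Working it through.** **Inputs.** Difference 6 mm, standard deviation 4.5 mm, 16/8 planned (Protocol 9.1); 1:1 used (SAP 3.3), taken as 12/12; cut-offs 0.05, 0.025, 0.0125 (Protocol 9.6.2, SAP 9.2.1).

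**Step 1: reproduce the stated figure.** For a two-sample t-test the non-centrality is (6/4.5)/√(1/n₁ + 1/n₂), with n₁ + n₂ − 2 degrees of freedom.

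- 16/8: 1.333/√0.1875 = 3.08 on 22 df. Power at 5% is 83.7%, agreeing with the stated 83%.
- The same formula, rounded up to multiples of three, reproduces all 14 sizes in Table 9-1.
- 12/12: 1.333/√0.1667 = 3.27 on 22 df. Power at 5% is 87.7%, so the SAP is right that 1:1 increases power.

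Write F(a) for the power of one test at level a:

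| Subjects | F(0.05) | F(0.025) | F(0.0125) |
|---|---|---|---|
| 16/8 | 0.837 | 0.745 | 0.641 |
| 12/12 | 0.877 | 0.798 | 0.704 |
| 11/11 | 0.845 | 0.754 | 0.650 |

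**Step 2: power for one type under the step-up rule.** For three independent tests with last cut-off c, type 1 is declared with probability

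F₁(.05)F₂(.05)F₃(.05) + F₁(.025)[F₂(.025)(1−F₃(.05)) + F₃(.025)(1−F₂(.05))] + F₁(c)[(1−F₂(.025))(1−F₃(.025)) − (F₂(.05)−F₂(.025))(F₃(.05)−F₃(.025))],

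where F(a) = a for a type with no effect. At 12/12 and c = 0.0125:

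- Three types respond: 0.675 + 0.157 + 0.024 = 0.856.
- Two respond: 0.038 + 0.608 + 0.137 = 0.783.
- One responds: 0.002 + 0.038 + 0.668 = 0.709 (unrounded terms).

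| Subjects per type | Three respond | Two respond | One responds |
|---|---|---|---|
| 16/8 | 80.4% | 72.4% | 64.7% |
| 12/12 | 85.6% | 78.3% | 70.9% |
| 11/11 (2 of 24 lost) | 81.3% | 73.3% | 65.5% |

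Simulation agrees with the closed form. A correlation of 0.5 between the three test statistics at 12/12 gives 84.1%, 77.6% and 70.8%, so independence does not drive the result.

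**Step 3: how firm the lower figures are.**

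- *Last cut-off.* With 0.05/3 = 0.0167 at the last step, the one-responder figure at 12/12 is 74.7%. So about 4 points of the shortfall come from the 0.0125 cut-off, which is a separate matter.
- *Numbers per type.* The 12/12 is not established. The analysis sets in SAP 6.1 are defined by the lesions present, not by sub-group, and SAP 3.2 warns: "Notice that a subject can be included in the analysis of more than one type of lesions". Protocol 4.2.2 stratifies randomisation by site only, so balance within a type is not assured. Under the written rule the one-responder figure runs from 59.5% at 10/10 to 75.6% at 13/13 and 83.2% at 15/15.
- *Losses.* SAP 9.2.1 uses the early end-of-treatment MRI of subjects who stop during or after cycle 2 and imputes the rest, so a discontinuation is not automatically a lost subject. Imputation alone recovers little information.

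**The case for a change.** The strongest argument for a change is that SAP 3.3 was reopened after last patient last visit precisely to comment on power, and stopped at a favourable direction without a number. One more sentence would cost almost nothing and would guard against over-reading a non-significant lesion type. The lower figures are real, and they apply to a situation that the trial was partly built to explore.

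Part of this stands: the 83% is not the power of the decision rule, and neither document says so in words. The rest carries less weight. The test, level, split and number are written beside the figure, so its basis is not hidden. Identifying the type that responds best is compatible with all three responding to different degrees; the 78% and 71% need one or two types to have exactly no effect, which departs from the declared planning assumption. A sentence built on 12/12 would also put a hypothetical number into a document written when actual counts per type could be obtained. A non-significant type will be judged from the treatment difference and 95% confidence interval that SAP 9.2.1 requires, not from planning power.

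**Conclusion.** The concern does not call for a change. The 83% and both sample size tables are correct as figures per comparison, before Hochberg, at 2:1 and with all 24 subjects observed. Under the documents' equal-effect assumption, independent types and complete data, power per type under the written rule is about 80% at the planned 16/8 and about 86% at an assumed 12/12, so the stated level is met at the ratio used. With 2 of 24 lost and equal effects it is still about 81%, under 2 points below the stated figure. Power is clearly lower, about 78% or 71% at 12/12, only if one or two types do not respond at all. No gain from ANCOVA adjustment is counted in any of these figures.

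Sample size and allocation were already fixed when this SAP was written, and the analysis, the decision rule and the reported intervals would be the same with or without extra power figures. What is missing is a label that a statistician supplies on reading the section.

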9.2 Subject Disposition

All subjects screened and randomised will be accounted for. Screened subjects who discontinue from the trial prior to randomisation are regarded as screening failures. The number of screened but not randomised subjects will be summarised by primary reason for screening failure.

Subject disposition with respect to analysis set will be tabulated by treatment group for all randomised subjects.

All premature discontinuations will be summarised and listed by time of and reason for discontinuation. The treatment group difference in the proportion of subjects who discontinue will be tested using the Fishers exact test.

9.3 Protocol Deviations

Major protocol deviations, such as significant non-compliance or other serious unforeseen deviations deemed to invalidate the data and affect the conclusions of the trial, will lead to exclusion of data from the per protocol (PP) analysis set. Data will not be excluded from the PP analysis set in case of minor protocol deviations. The list of major protocol deviations includes, but is not restricted to:

- Treatment received not in accordance with randomisation
- Non-compliance with IMP treatment regimen for >20% of days during the non-menstrual period

The detailed criteria of major protocol deviations will be further defined in the SAP. Unforeseen deviations deemed to impact the primary endpoint of the trial may additionally be rated as major protocol deviations by the Ferring clinical team on the basis of a blinded review of data before declaration of clean-file and lock of database.

The list of major protocol deviations will be detailed and documented in the clean file document prior to database release.

9.4 Analysis Sets

9.4.1 Full Analysis Set (FAS)

The FAS comprises all randomised and treated subjects and is analysed according to the planned treatment.

9.4.2 Per Protocol (PP) Analysis Set

The PP analysis set is defined as all randomised subjects except those with a major protocol deviations as described in section 9.3.

9.4.3 Safety Analysis Set

The safety analysis set comprises all treated subjects and is analysed according to the actual treatment received.

9.5 Trial Population

9.5.1 Demographics and other Baseline Characteristics

All relevant baseline data will be summarised in tables by treatment groups and in total. In addition summary tables will be presented by trial site.

The purpose of these tabulations is to characterize the treatment groups and assess the degree of similarity achieved by the randomization. Baseline data will not be compared using statistical tests. Unless otherwise noted, tabulations will be produced for FAS.

Continuous variables will be presented with number of subjects, mean, standard deviation, median, inter-quartile range, minimum, and maximum. Categorical variables will be presented with number and percentage of subjects within each specific category.

9.5.2 Medical History, Concomitant Medication and Other Safety Evaluations

Medical history will be coded using MedDRA. The version of MedDRA will be documented. Medical history will be listed by subject and summarised by System Organ Class (SOC) and preferred term.

Prior and concomitant medication will be summarized by ATC classification 1st level (alphabetically), ATC classification 2nd level (in decreasing order of frequency) and treatment group.

Other baseline evaluations including menstrual history, reproductive history, body measurement and vital signs will be presented by descriptive statistics by treatment group.

